Study Background and Rationale: Among patients receiving opioids for noncancer pain, recent research in North America showed a strong association between doses and opioid-related mortality, especially at dosages exceeding thresholds recommended in recent guidelines. However, the focus on over-dosage may underestimate overall opioid-related mortality and data on death associated with opioid use in a population-based cohort of chronic noncancer pain patients in Europe is scarce. Especially comparative studies studying the safety of long-term opioid therapy in a real-world setting relative to non-opioid medication for chronic noncancer pain are needed in a European context.

Research Question and Objective(s): The primary objective is to investigate the association between mortality among patients with chronic noncancer pain with long-term opioid-therapy compared to non-opioid pain medication. The secondary objectives are to determine the risk of addiction/abuse and hospital admissions among opioid users with chronic non-cancer pain compared to patients with non-opioid pain medication.

Study Design/Type: This is a cross-sectional observational cohort study between 2012 and 2017 of patients with chronic noncancer pain.

Study Population and Data Resource: The data will be retrieved from an anonymized German health claims database including 4,00,000 persons insured by 69 German statutory health insurances. The data set includes 5.0% of the population covered by statutory health insurances

from January 1, 2012, to December 31, 2017. Only anonymized and aggregated data (no directly or indirectly identifying data) will be extracted.

Summary of Patient Eligibility Criteria: From the data extraction, the cohort will be analysed according to the following criteria:

Inclusion criteria: At least one diagnosis of pain R51 (headache), R52* (pain, not elsewhere classified), M00 – M99 (Diseases of the musculoskeletal system and connective tissue), G43* (migraine), G44* (other headache syndromes), G50.0 (trigeminal neuralgia), G50.1 (atypical facial pain), F45.4* (persistent somatoform pain disorder), G62* (polyneuropathies), E10.4*-E14.4 plus G63.3 (diabetes mellitus with neurological complications) in at least 3 quarters between 01.01.2012 and their first opioid claim AND opioid medication (Cohort A) OR non-opioid medication (Cohort B) between 01.01.2012 and first pain medication claim.

Exclusion criteria: Patients with previous prescription of opioid medication or non-opioid medication between 01.01.2012 and index treatment will be excluded. Patients with cancer treatment, palliative care or opioid substitution after index treatment will be excluded.

Follow-up: Patients' follow-up period include 5 years after start of opioid resp. non-opioid treatment and chronic pain diagnosis between 01.01.2013 and 31.12.2017. Each patient will be censored at death (death date), switching of study group (opioid --> non-opioid or vice versa), 12 months without treatment or followed-up 5 years until last known record for the patient in the German health claims database, latest at 31.12. 2017 (end of latest data cut), whichever happens first.

Variables:

Outcome Variables include death by any course as primary endpoint and hospitalization due to any course, hospitalization with misuse, addiction diagnoses, outpatient diagnosis of misuse or addiction and treatment procedures as secondary endpoints.

Exposure Variables are pain treatments including opioid and non-opioid treatments.

Other Covariates will be collected for assessments over the course of the study: Age and gender (sex: male, female), charlson comorbidity index. Comorbidities, comedications, region will be collected for Propensity Score Matching.

Data Analysis: The main analysis will focus on each of the 2 main cohorts with chronic pain patients as defined at inclusion and:

- with opioid treatment between 01.01.2013 and 31.12.2017 (named cohort A)
- with non-opioid treatment between 01.01.2013 and 31.12.2017 (named cohort B)

To address the group comparisons adequately, a propensity score matching will be conducted. The main analyses will include a multivariate Cox proportional hazards regression. Additional stratified analyzes will be carried out as follows: Subgroup analyses for each following pain conditions will be conducted: headache (R 51*); pain, not elsewhere classified (R52*); persistent somatoform pain disorder (F45.4*); polyneuropathy in diabetes (E10.4*-E14.4 plus G63.3), kyphosis and lordosis (M40), scoliosis (M41), spinal osteochondrosis (M42), other deforming dorsopathies (M43), ankylosing spondylitis (M45), other inflammatory spondylopathies (M46), spondylosis (M47), other spondylopathies (M48), and spondylopathies in diseases classified

elsewhere (M49), Cervical disc disorders (M50), thoracic, thoracolumbar, and lumbosacral intervertebral disc disorders (M51), Other and unspecified dorsopathies, not elsewhere classified, and dorsalgia (M54).

5. Protocol amendments and Updates

Table 5-1: Protocol amendments and updates

Version	Description	Name / Author	Date
V.01	First draft	LinkCare GmbH	10 September 2018
V.02	Amendments following TCs and mails with the other authors	LinkCare GmbH	31 October 2018
v.03	Amendments following e-mail of [name] GmbH	28 November 2018

6. Milestones

Table 6-1: Milestone plan

Milestone	Planned date
Finalization of study design	30. September 2018
Writing of a detailed analytical protocol/ study plan	15. November 2018
Contracting with German health insurances	15. November 2018
Data obtaining, quality assurance and data analysis	31. January 2019
Writing of publication	28. February 2019
Submission and peer-review process	31. March 2019
Publication	31. July 2019 (dependent on journal)

7. Rationale and Background

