9.1 Study Design

This is a retrospective observational cohort study based on an anonymized German health claims database. This database contains data on around 4 million insured people from 69 German statutory health insurances (SHI). This research database is a complete, longitudinal claims dataset of approx. 7 million individual patients (ca. 10% of the statutory insured population of Germany) between 2012 and 2017. The analyses for this study will be done on a 4 million patients subset that is stratified by age

and gender based on the 2013 population structure of Germany as reported by the German Federal Statistical Office DeStatis.

This study consists of two cohorts: opioid and non-opioid patients. Only patients who started their therapy between 2013 and 2017 and had no therapy in 2012 (therapy naïve patients) will be included in the study.

Exposure time is defined as max. 5 years after the initial prescription for each patient, so that exposure time is max. 60 months per patient.

Exposure time may end before the end of study if patient died, stopped treatment (end of follow-up after 1 year without treatment with opioids / other pain medication), changed treatment group (from opioids to other pain medication or vice versa) or was lost to follow up due to other reasons (e.g. change of insurance), whichever occurs first.

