9.2.1 Study Period

Due to data protection regulations in Germany, only an extract of maximum 6 years of data coverage could be available for the research purposes: 1st January 2012 to 31st December 2017.

The **baseline period** is defined as the period prior to the date of first diagnosis of diagnoses or first opioid or non-opioid treatment initiation as described in inclusion criteria (Chapter 9.2.2.1). The baseline assessment period endures between January 01, 2012 and first study medication prescription.

Index treatment is defined as the date of first opioid or non-opioid treatment prescription between 1st January 2013 and 31st December 2017.

Exposure time is defined as time between index treatment and December 31, 2017. Considering data availability of a maximum of 6 years and prescription in a required time period of 60 months, exposure time endures maximum five years. Thus, patients can be censored at death (death date in the linked records), last known record for the patient in the German health claims database, switching of treatment groups (from opioid group to non-opioid group or vice versa), 12 months without opioid/non-opioid treatment or 31st December 2017 (end of latest data cut), whichever comes first.

[figure not shown]
The **outcomes** will be assessed between index treatment and 31.12.2017.

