9.2.2 Patient Eligibility

9.2.2.1 Inclusion Criteria

For the purposes of this study, the requested extraction of the database consists of population of patients with chronic non-cancer pain corresponding to the following criteria. Inclusion and exclusion criteria are also provided in Figure 2.

Figure 2: Inclusion and exclusion criteria

Cohort A

- Patients are included in the long-term opioid group if they started an opioid-therapy between 2013 and 2017 and received consecutive prescriptions for opioid medications over a minimum of 3 quarters, over a 60-month period between January 1, 2013, and December 31, 2017. The treatment will be assessed using the ATC codes of opioid treatment N02AA01, N02AA05, N02AB03, N02AE01, N02AX02, N02AX01, N02AX06 (see also Table 9-1) reported in reimbursed medicines to patients.

- Patients are only included if they have been diagnosed in at least three quarters in the study period with one of the following diagnoses: R51, R52*, M00*-M99*, G43*-G44*, G50.0 or G50.1, F45.4*, G62*, or E10.4*-E14.4 plus G63.3. At least one diagnoses must be between 1 January 2012 and index treatment and main and secondary hospital diagnoses (*i.e. Haupt- und Nebendiagnosen*) will be used to include the patients.

Cohort B

- Patients with non-opioid pain medication are included, if they received a medication therapy with anticonvulsants (gabapentin, pregabalin, carbamazepine), antidepressants or non-opioid analgesics (NSAIDs, Metamizole) over a minimum of 3 quarters, over a 60-month period between January 1, 2013, and December 31, 2017. The non-opioid treatment will be assessed using the ATC codes (N03AX12, N03AX16, N03AF01, see also Table 9-1) of treatment reported in reimbursed medicines to patients.
- Patients are only included if they have been diagnosed in at least three quarters in 2012 with one of the following diagnoses: R51, R52*, M00*-M99*, G43*-G44*, G50.0 or G50.1, F45.4*, G62*, or E10.4*-E14.4 plus G63.3. At least one diagnoses must be between 1 January 2012 and index treatment and main and secondary hospital diagnoses (*i.e. Haupt- und Nebendiagnosen*) will be used to include the patients.

All diagnoses that lead to patient inclusion when coded between 01.01.2012 and index treatment and in at least three quarters within the study period are provided in Table 9-2 below.

Table 9-1: List of ATC codes of study opioid and non-opioids

Name	ATC Code
Study opioids	
Morphine	N02AA01
Oxycodone	N02AA05
Fentanyl	N02AB03

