9.2.2.2 Exclusion Criteria

Following exclusion criteria will be used to extract the eligible study population (see also Figure 2):

Cohort A and B:

- Patients with present opioid and non-opioid pain medication prescriptions in 2012 are excluded from analysis (therapy-naïve patients only).
- Cancer patients will be excluded if the cancer diagnosis is accompanied by at least one of the following treatments in the same quarter: radiation therapy or chemotherapy all defined by the codes in Table 9-3. Diagnoses will be assessed via ICD-10 diagnoses during the inclusion period from 1 January 2012 until index treatment and main and secondary hospital diagnoses (i.e. *Haupt- und Nebendiagnosen*) will be taken into account.
- Palliative care, coded by ICD-10 code Z51.5 or OPS code 8-982*, 8-98e*, 8-98h* before index date is excluded
- Opioid substitution treatment with ICD-10 code Z51.83 in the study period is excluded.

Table 9-3: Exclusion criteria for cancer patients

Name	ICD-10 Code	
Malignant neoplasms	C00-C97	
Plus at least one the following in the same quarter		
Name	Code	Type of Code
Palliative care	Z51.5	ICD-10
Chemo therapy	Z51.1	ICD-10
Radiation therapy	Z51.0	ICD-10
Chemo therapy	8-541* 8-542* 8-543* 8-544* 8-546*	OPS Code

Radiation therapy	8-52*	OPS Code
Palliative care	8-982* 8-98e* 8-98h*	OPS Code

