9.3 Risk adjustment

9.3.1 Propensity Score Matching

For the planned analyses, patients with opioid and non-opioid treatment need to be comparable. Mortality rates are expected around 100 and 200 per 10,000 persons years⁸ thus limiting the number of covariates for risk-adjustment to avoid over-fitting (10:1 rule of thumb: Not more than 1 predictor/covariate for 10 events). To avoid this overfitting problem but still be able to adjust for a large number of covariates, a propensity score (PS) matching will be conducted before the acutual Cox regression.

PS-Matching will be based on logistic regression and reflect the probability of getting an opioid treatment considering the following risk factors. The choice of covariates is based on a previous retrospective cohort study about opioid dependency and mortality in the US⁹ (see Appendix A, for the list of study covariates based on Ray et al.)

- region (i.e. 'Bundesland')
- comorbidities: obstructive sleep apnoea, depression and other comordidities
- comedication with other anticonvulsants than gabapentin, pregabalin or carbamazepine, comedication with neuroleptics, NSAR, tranquilizer or muscle relaxants, metamizole, comedication

⁸ Numbers from Ray et al. (2016)

⁹ Ray et al., 2016

with cannabinoid drugs, year of index treatment and drug dosage of the opioids/non-opioids as defined in section 9.4.

- medical procedures based on OPS-codes assessed as a number of procedures (see Appendix B, for the list of OPS codes), e.g. dialysis

PS matching will be based on a logistic regression (logit model) and reflects the likelihood that a patient will be prescribed by opioid medication if certain risk factors/comorbidities are considered. All binary predictors are included in the model as dummy variables (1 vs. 0). The influence of each variable is given as odds ratios with 95% confidence intervals.

The following equation will be employed for PS matching:

$$P_i = \frac{e^{\beta_0 + \sum_{j=1}^n \beta_j x_{j,i}}}{1 + e^{\beta_0 + \sum_{j=1}^n \beta_j x_{j,i}}}$$

The dependent variable is the treatment and will be dummy coded as 1 (opioid treatment in index year) and 0 (no opioid treatment) (P_i).

Age and gender will also be used for risk adjustment and will be assessed using national insurance data, for age by date of birth and is calculated based on the index treatment. For age, a variance of 5 years is allowed, i.e. the age can vary by plus / minus 5 years when matching.

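### Cohort, index date and propensity label follow rules that do not agree, so a patient who moves from a non-opioid to an opioid has no fixed place in the comparison

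*Protocol*

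**What the plan says.** Five parts of the protocol bear on where a patient belongs and when follow-up starts.

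- **Naive rule.** The synopsis, under exclusion criteria: "Patients with previous prescription of opioid medication or non-opioid medication between 01.01.2012 and index treatment will be excluded". Section 9.2.2.2: "Patients with present opioid and non-opioid pain medication prescriptions in 2012 are excluded from analysis". Section 9.1 likewise asks only for a drug-free 2012: "had no therapy in 2012 (therapy naïve patients) will be included in the study".
- **Index date.** Section 9.2.1: "Index treatment is defined as the date of first opioid or non-opioid treatment prescription between 1st January 2013 and 31st December 2017". This is the first drug of either class, whichever cohort the patient belongs to. Section 9.3.2, when defining age, starts the same window in 2012.
- **Cohort entry.** Section 9.2.2.1: "Patients are included in the long-term opioid group if they started an opioid-therapy between 2013 and 2017", with consecutive prescriptions over at least three quarters. Cohort B needs a listed non-opioid over at least three quarters in 2013-2017. Neither criterion bars the other class or refers to the class of the index drug.
- **Propensity outcome.** Section 9.3.1: "dummy coded as 1 (opioid treatment in index year) and 0 (no opioid treatment".
- **Switching.** Section 9.1 ends exposure time if the patient "changed treatment group (from opioids to other pain medication or vice versa". The synopsis and Section 9.2.1 agree. The mortality-rate definition in Section 9.4.2.1 lists neither switching nor the 12-month treatment gap among its censoring events.

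NSAIDs and metamizole are Cohort B drugs in Table 9-1 and also comedication covariates in Section 9.3.1.

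**The concern.** Stepping up from an NSAID, metamizole, an antidepressant or an anticonvulsant to an opioid is an ordinary course in chronic pain, so the rules must place such patients without ambiguity. Here cohort depends on what the patient took at any time in 2013-2017, the index date on the first drug of either class, and the propensity label on the calendar year of index.

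At stake is the primary mortality comparison. If a patient counts in Cohort A from an index date set by a non-opioid, the interval up to the opioid is time that had to be survived to enter the cohort. It adds person-time without deaths to the opioid group. If the propensity label follows opioid use later in the index year, the matching model is fitted to an outcome that differs from the groups being compared and that depends on events after baseline.

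**Working it through.** The protocol gives no figure to reproduce on this point, so the check applies the written rules to hypothetical prescription histories. All three have a drug-free 2012 and are assumed to meet the diagnosis criteria.

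| History | Drug criteria met (9.2.2.1) | Index (9.2.1) | Propensity label (9.3.1) | Months from index to first opioid |
|---|---|---|---|---|
| 1. NSAID from January 2013 through 2014; opioid for three quarters from January 2015 | A and B | January 2013 | 0 | 24 |
| 2. NSAID for three quarters from January 2014; opioid for three quarters from October 2014 | A and B | January 2014 | 1 | 9 |
| 3. One NSAID claim in February 2013; opioid for three quarters from February 2016 | A only | February 2013 | 0 | 36 |

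**Naive rules.** All three pass the 2012 rule. With the Section 9.2.1 index they also pass the synopsis rule, because nothing can precede the first drug of either class from 2013. If index means the opioid start, all three fail the synopsis rule. That rule therefore excludes either no step-up patient or every one, depending on a definition it does not supply.

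**History 1.** Placed in Cohort B and censored at the switch, it gives 24 months of non-opioid time and no bias. Placed in Cohort A, either the 24 months count as opioid time, or the move to the opioid is treated as a switch and follow-up ends before any opioid exposure.

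**History 2.** The index drug is an NSAID, yet the label is 1 because of a prescription nine months later.

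**History 3.** Only Cohort A can take this patient, so there is no choice of cohort to make, and the rules still conflict. If the 12-month gap rule runs from the 2013 claim, follow-up ends about February 2014. The patient then contributes about 12 months to Cohort A, none of it on an opioid. If the gap rule is not applied, as in the Section 9.4.2.1 list, the pre-opioid time is 36 months. The label is 0 for a Cohort A patient.

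**Possible size where pre-opioid time is counted as opioid time.** Let f be the share of Cohort A with an earlier non-opioid, L the pre-opioid years per such patient, and T the mean years of follow-up after opioid start. No deaths can fall in the added time, so

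apparent opioid rate / true opioid rate = T / (T + f × L).

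The protocol gives none of the three; all values below are assumptions.

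- First-drug assignment with switch censoring (f × L = 0): ratio 1.00
- f = 10%, L = 0.5, T = 2.5: 2.5 / 2.55 = 0.98
- f = 25%, L = 1, T = 2.5: 2.5 / 2.75 = 0.91
- f = 50%, L = 2, T = 1.5: 1.5 / 2.5 = 0.60

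With roughly constant hazards and an unaffected Cohort B, a true hazard ratio of 1.0 would appear as about these values.

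**The case against.** The strongest reply is that two coherent readings exist and neither produces immortal time. If cohort follows the first drug, the step-up patient is in Cohort B until the opioid starts and is then censored. If index is specific to the class, follow-up begins at the opioid, as the synopsis suggests when it counts five years from the start of the respective treatment, and the synopsis naive rule removes the patient. The bias needs the index date of one reading combined with the cohort of the other. The criteria are also said to appear in Figure 2, which is not in the available text.

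This reply limits the size and certainty of the bias, but does not remove the conflict. The two readings give different study populations and the text chooses neither. History 3 is eligible for Cohort A under Section 9.2.2.1, with an index date before its first opioid under Section 9.2.1. A figure might show the intended assignment, but the written rules would still contradict it or each other. Index date, cohort entry and propensity outcome are also fixed in this protocol, so the conflict is not detail left to an SAP.

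Other parts of the reply stand. The index-year wording may be a loose way of saying treatment at index. Comedication covariates and censoring at a change of group are compatible if adding a drug is not a change; the protocol only needs to say so.

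Two stronger conclusions might be inferred and are not supported. The first is that patients will be analysed twice: meeting two sets of criteria concerns eligibility, and censoring at a change of group presupposes one group at a time. The second is that the two naive rules by themselves select different patients: under the Section 9.2.1 index they coincide, however cohorts are assigned.

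**Conclusion.** The point holds as an inconsistency among cohort entry, index date and propensity label. Applied together as written, the rules can start Cohort A follow-up before opioid exposure, end it before exposure begins, or let a prescription after index set the propensity label. The synopsis naive rule does not settle the matter.

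The size is not derivable from the protocol. It runs from none, under first-drug assignment with switch censoring, upward; the ratios of 0.98 to 0.60 rest on assumed shares and durations. A reader might take them as an estimate of the bias in this study, which they are not. The direction is clear only where pre-opioid time is counted as opioid time: the opioid mortality rate is understated, which favours opioids in a safety comparison. Because the conflict decides who is compared and from when on the primary endpoint, and the remedy is cheap, it should be resolved before the cohorts are extracted.

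**What to change.** State one rule, in the same words, in the synopsis and Sections 9.2.1, 9.2.2 and 9.3.1:

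1. **Index date:** first dispensing of any Table 9-1 drug from 1 January 2013, with none in 2012. Align the age definition in Section 9.3.2 with it.
2. **Cohort:** class of the index drug.
3. **Propensity outcome:** cohort membership, A = 1 and B = 0.
4. **Later movement between classes:** handled only by the existing switch-censoring rule, which should also be listed in the mortality-rate definition in Section 9.4.2.1.
5. **Two clarifications for the authors to decide:** whether a non-opioid added to a continuing opioid counts as a switch, consistent with its use as a comedication covariate; and how patients who start both classes on the same day are assigned.

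The editing cost is small, but cohort membership changes. Step-up patients leave Cohort A and contribute to Cohort B only until the switch. A patient like history 3, with one non-opioid claim, would fall in neither cohort. Cohort A becomes smaller and describes patients whose first study drug was an opioid, which the report should say.

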- **Quarter of index treatment:** Quarter in which index treatment was initiated, wheras Q1/2012 is quarter=1, Q2/2012 is quarter=2 and so on.
- **Propensity Score** as calculated before

¹² Yurkovich et al 2015

¹³ Quan et al 2011

Table 9-4: Charlson Comorbidity Index

Condition	Scale	Points	ICD-10-GM Code
Myocardial infarction	No	0	
	yes	1	I21*-I22*, I25.2
Congestive Heart Failure	No	0	
	yes	1	I50*
Peripheral vascular disease	No	0	
	yes	1	I73*, I74.2, I74.3, I74.4, I71.3, I71.5, I71.4, I71.6
Cerebrovascular accidents	No	0	
	yes	1	I60*-I69*
Dementia	No	0	
	yes	1	F00*-F03*, F05.1
Chronic obstructive pulmonary disease	No	0	
	yes	1	J44*
Rheumatic disease	No	0	
	yes	1	M05*, M06*, M31.5, M32-M34, M35.3, M45*,
Peptic ulcer disease	No	0	
	yes	1	K25*, K26*, K27*, K28*
Liver disease	No	0	
	Mild	1	K70.1-K70.3, K70.9, K71-K71.0, K71.2-K71.8, K73*, K74.0, K74.2, K74.6, K74.3, K74.4, K74.5
	Severe	3	K70.4, K71.1, K72*, K76.3
Diabetes mellitus	No	0	
	Un-complicated	1	E10.9*, E11.9*, E13.9*, E14.9*, E10.1*, E11.1*, E13.1*, E14.1*
	Complicated / end organ damage	2	E10.2*, E11.2*, E13.2*, E14.2* E10.3*, E11.3*, E13.3*, E14.3* E10.4*, E11.4*, E13.4*, E14.4*, E10.5*, E11.5*, E13.5*, E14.5*
Hemiplegia	No	0	
	yes	2	G81*
Kidney diseases	No	0	
	yes	2	N17*-N19*
Cancer	No	0	
	Solid	2	C00*-C76*, C80*, C81*, C82*, C83*, C84*, C88.3, C88.7, C88.9, C96*, C90.1, C91*-C95*, C81*, C82*, C83*, C84*, C85*, C86*, C88*
	Metastatic	6	C77*, C78*, C79*, C80*
AIDS / HIV	No	0	
	yes	6	B20* - B24*
Demographics as risk factors			
		Hazard Ratio	
age (> 65 years)		4,40	
gender (male)		1,28	

The Cox proportional hazards model will use treatment dosage as time-varying covariates, re-calculating it annually during follow up. The model will also be adjusted for age, gender, CCI at the baseline. Covariates will not be treated as time varying variables.

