9.4.2.1 Primary endpoint

Primary endpoint is **death** by any course in the study follow-up. Death will be assessed during the follow-up period by number of patients who deceased during follow-up period (2013 – 2017) via the date of death in German claims data base. Additionally, mortality rate will be estimated as number of patients who died during the follow-up divided by person-time

of follow-up, censoring at time of death, last known record for the patient in the database, or 31st December 2017 (end of latest data cut), whichever is earlier.

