9.8.2 Sensitivity analysis

The following main sensitivity analysis will be conducted:

Sensitivity analysis
No cancer patients: Exclude all patients with at least one C00 – C96 diagnosis before index date

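### Censoring at a treatment-group switch may be informative for death, the one listed sensitivity analysis cannot reveal it, and the mortality-rate definition contradicts the rule

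*Protocol*

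**What the plan says.** The abstract (Follow-up) censors patients at, among other events, "switching of study group (opioid --> non-opioid or vice versa), 12 months without treatment". Section 9.1 ends exposure time at a change of treatment group, and section 9.2.1 repeats the rule as "switching of treatment groups (from opioid group to non-opioid group or vice versa), 12 months without opioid/non-opioid treatment".

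On the endpoint, the abstract states: "Outcome Variables include death by any course as primary endpoint". On the model: "The main analyses will include a multivariate Cox proportional hazards regression", fitted after propensity score matching. Section 9.3.2 recalculates dosage each year but otherwise says "Covariates will not be treated as time varying variables".

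Section 9.4.2.1 describes the follow-up behind the mortality rate differently. There the denominator is person-time "of follow-up, censoring at time of death, last known record for the patient in the database, or 31st December 2017". Neither a switch nor a 12-month gap is on that list.

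Section 9.8.2 lists one sensitivity analysis: "No cancer patients: Exclude all patients with at least one C00 – C96 diagnosis before index date". The limitations in 9.10 do not mention switching.

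**The concern.** Cox regression needs censoring that is independent of death given the covariates in the model. A patient on non-opioid treatment whose health worsens may be given an opioid shortly before dying. If that prescription counts as a switch, follow-up stops and the death drops out of Cohort B's hazard. It does not reappear in Cohort A. Index is the first study prescription of either kind (9.2.1), the abstract excludes earlier users, and Cohort A requires prescriptions over at least three quarters (9.2.2.1).

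The model cannot correct for this. Comorbidity is fixed at baseline. The quantities in 9.3.2 that reach past index, dosage and treatment duration, do not measure deterioration.

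If such losses are more frequent in Cohort B than in Cohort A, the primary hazard ratio moves against opioids for a reason unrelated to their safety. The listed sensitivity analysis would leave the shift unseen, because it changes who enters the cohorts and not when follow-up ends.

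**Working it through.** The Protocol states no event count, target hazard ratio or switching rate, so there is no figure of its own to reproduce. The sizes below are illustrations.

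**Formula.** Let f_A and f_B be the shares of deaths in each cohort that are preceded by a censoring switch. If the switch comes shortly before death, little person-time is lost, and each observed hazard is about (1 − f) times the true one:

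observed HR ≈ true HR × (1 − f_A) / (1 − f_B)

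**Loss in Cohort B only (f_A = 0).**

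| f_B (assumed) | Factor | Observed HR, true HR 1.00 | Observed HR, true HR 1.50 |
|---|---|---|---|
| 5% | 1/0.95 | 1.05 | 1.58 |
| 10% | 1/0.90 | 1.11 | 1.67 |
| 20% | 1/0.80 | 1.25 | 1.88 |
| 30% | 1/0.70 | 1.43 | 2.14 |

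**Loss in both cohorts, true HR 1.00.**

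- f_A = f_B = 20%: 0.80/0.80 = 1.00, so no bias.
- f_A = 10%, f_B = 20%: 0.90/0.80 = 1.125.
- f_A = 20%, f_B = 10%: 0.80/0.90 = 0.89, so the direction reverses.

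The bias therefore comes from the difference between the cohorts.

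**Simulation check.** Inputs from the Protocol were death hazards of 0.01 and 0.02 per year (the 100 and 200 per 10,000 person-years in 9.3.1) and follow-up of at most five years. Assumed inputs were 60,000 patients per cohort, uniform index dates, 10% per year non-informative switching, and a pre-terminal switch 0 to 3 months before death in Cohort B only. With a true HR of 1.00, Cox fits censored at the switch gave the following at the lower and higher hazard:

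- f_B = 0%: 1.06 and 1.01
- f_B = 10%: 1.21 and 1.08
- f_B = 20%: 1.19 and 1.30
- f_B = 30%: 1.42 and 1.44

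Each value is a single run with Monte Carlo error of roughly 3–5%, so the values support the formula's direction and approximate size but not its second decimal. Following the same patients by starting cohort gave 0.96 to 1.05. With 20% lost in both cohorts, the censored estimate (1.09) and the as-started estimate (1.08) agreed; their shared distance from 1 is sampling noise. In these runs the switch did not change the death hazard, so no cross-over dilution was simulated.

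**The follow-up definitions side by side.** The abstract, 9.1 and 9.2.1 end follow-up at a switch and after 12 months without treatment. Section 9.4.2.1 ends it at death, last record or 31 December 2017. Under the first rule a death after a switch is not counted; under the second it is. As written, the mortality rate and the hazard ratio can rest on different deaths and different person-time, with no explanation.

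**The case against.** **A statistical analysis plan may add analyses.** It is not shown, and 9.8.2 calls its list the main sensitivity analysis, which does not exclude others. This stands as far as omitted detail goes. But the Protocol itself fixes the censoring rule in three places and then contradicts it in 9.4.2.1, so the point concerns what it fixes.

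**A switch is not defined as a first opioid claim.** The wording refers to changing group, and membership of the long-term opioid group needs consecutive prescriptions over at least three quarters (9.2.2.1). If a switch means meeting that definition, a short opioid course before death would not censor anyone. This stands, and it makes the mechanism conditional.

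**Section 9.4.2.1 already keeps deaths after a switch.** Read literally it does, so they are not lost from every output. But it yields a crude rate, not a second adjusted hazard ratio.

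**The palliative-care exclusion may remove some of these patients.** The abstract places it after index, while 9.2.2.2 places it before. How many end-of-life switches remain depends on which text applies. Under the abstract's text, patients would instead be removed because of later events.

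**A reader might infer that deaths are removed from Cohort B alone, or that a step up to opioids often precedes death, so that a spurious excess is certain.** The documents support neither. The rule works in both directions, the 12-month gap applies to both cohorts, and there is no figure on switching or on opioid starts before death.

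**Conclusion.** The point holds in conditional form. The Protocol censors an all-cause-death Cox model at an event that may be related to impending death, has no covariate that tracks deterioration, and lists no analysis that would show how far the hazard ratio depends on the rule. If Cohort B loses a larger share of deaths to switching than Cohort A, the estimate moves against opioids: about 1.05 to 1.43 under a true HR of 1 when 5% to 30% of Cohort B deaths are lost and none in Cohort A. The shares, the short lead time and the absence of loss in Cohort A are assumptions. Equal loss gives no bias, and greater loss in Cohort A reverses the direction. The size in this study is unknown.

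The contradiction between 9.4.2.1 and the abstract, 9.1 and 9.2.1 needs no assumption and should be corrected in any case. The on-treatment analysis remains a reasonable primary; the point does not show it to be wrong.

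**What to change.** Keep the on-treatment Cox model as primary, and make these changes:

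- In 9.8.2, add an as-started Cox analysis on the same matched cohort, with no censoring at a switch or at treatment stop.
- Report by cohort the number of switches and the deaths soon after a switch.
- Interpret any excess mortality in light of both estimates.
- State which prescription event counts as a switch, including whether adding a drug from the other group without stopping the first one counts.
- Align the follow-up in 9.4.2.1 with the abstract, 9.1 and 9.2.1. The hospitalization rate in 9.4.2.2 carries the same shorter list.
- Reconcile the abstract and 9.2.2.2 on the timing of the palliative-care exclusion.

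The cost is one further model run and a short table. Date of death and insurance dates are already among the database fields in 9.2; the extract must keep records after the switch. The downside is that cross-over dilutes the as-started estimate, so a value nearer 1 does not by itself show that the primary result is an artefact.

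Inverse-probability-of-censoring weights are optional, since they need time-updated covariates that the plan does not use. Attributing deaths within a fixed window after a switch to the original cohort is not advisable, because it could assign early opioid deaths to the comparator.
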